#### **6.7.3. Point of Exit**

Study Subjects may exit the study for a variety of reasons. The Investigator shall record the reason for ending participation in the study in the applicable Case Report Form. These reasons include, but are not limited to:

- Study completion (all study related visit(s) are completed)
- Withdrawal by the Subject
- Withdrawal by Investigator
- Lost to follow-up
- Death
- Study Termination

In the event of subject withdrawal or discontinuation prior to treatment visit (screen fail), study Subjects will be replaced until the desired enrollment is reached. In the event of subject withdrawal or discontinuation post treatment visit, Subject will not be replaced.

Data collected until the last known contact of study subject may be used in the analysis of study data. For study subjects lost to follow-up, the Investigator shall make 3 documented attempts before confirming the subject is lost to follow-up. If the study subject withdraws from the study for any reason and there is an ongoing safety event, additional safety event information may need to be collected by the Investigator and shared with Sponsor.

## **6.8. ROLE OF SPONSOR REPRESENTATIVE**

### **6.8.1. Monitoring**

Study monitoring is conducted to ensure that (i) the rights, safety, and well-being of study participants are protected, (ii) the reported study data are accurate, complete, and verifiable, and (iii) the conduct of the study is in compliance with the currently approved CIP, with good clinical practice (GCP) principles, and with applicable regulatory requirement(s). 3M, as Sponsor of this clinical investigation, is responsible for study oversight and for providing the Principal Investigators (PIs) and study staff with training regarding the proper conduct of the clinical investigation with regard to CIP adherence and validity of the data recorded on the CRFs. 3M has therefore assigned study monitor(s) to this clinical investigation. The progress of the clinical investigation will be monitored by:

- Periodic and/or remote review
- Telephone communications
- Review of CRFs and source documents (eg subject records)

The study monitor(s), other authorized representatives of the Sponsor, representatives of the IRB, or regulatory authorities may inspect all documents and records required to be maintained by the Investigator, including but not limited to Subject records (office, clinic, or hospital) for the participants in this study. The clinical study site personnel will permit access to such records. The Investigator will give 3M study monitor(s) direct access to source documents that support data on the CRFs, including any electronic records. If site policies restrict access to Subjects' files to site personnel, the PI will designate a staff member to work with the Sponsor's monitor to verify source documents on an as-needed basis. This verification will be conducted in a way that will ensure that only study-related information is examined.

Details of clinical site monitoring are documented in a Monitoring Plan (MP). The MP describes who will conduct the monitoring, the planned frequency of monitoring visits, records to be reviewed, and the distribution of monitoring reports.

Independent audits may be conducted by 3M personnel or an independent party to ensure monitoring practices are performed consistently across all participating sites and that monitors are following the MP.

#### **6.8.2. Other Sponsor Oversight**

In addition to study monitoring, the Sponsor, or their representatives may conduct the following tasks during this study:

- Audits of the Investigator
- Provision of technical support/product specific training for the study device

### **7. DATA MANAGEMENT**

Data collected for this study will be analyzed and stored at 3M or an approved supplier for use by researchers including those outside of the study. Permission to transmit, store and use data outside of the study will be included in the informed consent. Details of data management for this investigation are documented in a Data Management Plan (DMP). The DMP describes the procedures used for CRF tracking, data review, database cleaning, query management, coding and data reconciliation.

#### **7.1. DATA COLLECTION AND MANAGEMENT RESPONSIBILITIES**

Data collection is the responsibility of the clinical study staff at the site under the supervision of the site Investigator. The Investigator is responsible for ensuring the accuracy, completeness, legibility, and timeliness of the data reported.

All source documents should be completed in a neat, legible, permanent and un-editable manner to ensure accurate interpretation of data. Data recorded in the electronic case report form (eCRF) derived from source documents must be consistent with the data recorded on the source documents.

All data, including AEs and expected AE data, will be entered into a 21 CFR Part 11-compliant data capture system provided by the Sponsor. The data system includes password protection and internal quality checks (eg, automatic range checks) to identify data that appear inconsistent, incomplete, or inaccurate.

The Sponsor is responsible for compilation and verification of the clinical study data, retention of the clinical study database, performance of statistical analysis, and preparation of the clinical study report.

## 7.2. STUDY RECORDS RETENTION

Information for each study participant will be securely stored at each clinical site for internal use during the study. At the end of the study, all records will continue to be kept in a secure location in accordance with policies from the reviewing IRBs, Institutions, regulatory authorities, and Sponsor requirements.

No records will be destroyed without the written consent of the Sponsor. It is the responsibility of the Sponsor to inform the Investigator when study documents no longer need to be retained.

## 7.3. SPONSOR OVERSIGHT

The Investigator will allow access to clinical study records for periodic on-site or remote monitoring visits by a designated 3M representative, with the understanding that the representative is bound by professional secrecy and will not disclose the identity of any Subject or personal medical information. The representative will review eCRFs for completeness during monitoring visits and after the eCRFs are submitted; any discrepancies will be resolved with the Investigator or designee, as appropriate. The data will be entered into the clinical study database and verified for accuracy.

In addition to on-site or remote monitoring, routine review of submitted study information will be conducted by the Sponsor to ensure compliance with the CIP. Items reviewed include but are not limited to AEs, deviations, number of withdrawn/terminated Subjects, which all may impact the completion of the study. Appropriate measures may be taken to ensure Investigator compliance with the CIP.

## 8. STATISTICAL CONSIDERATIONS

### 8.1. PASS/FAIL CRITERIA

The null hypotheses that we seek to reject are that Vanish™ 5% Sodium Fluoride White Varnish has a 15.0 mm higher change from baseline VAS than Clinpro™ 2% Sodium Fluoride Aqueous Solution when measured immediately after application (within 15 minutes post-treatment) or at 24-hours after treatment ( $\pm 4$  hours). The null and alternate hypotheses are described below.

$H_0$ : Vanish™ Varnish changed from baseline – Clinpro™ 2.1% Sodium Fluoride Aqueous Solution change from baseline  $> 15$  mm.

$H_a$ : Vanish™ Varnish changed from baseline – Clinpro™ 2.1% Sodium Fluoride Aqueous Solution change from baseline  $\leq 15$  mm.

## **8.2. SAMPLE SIZE DETERMINATION**

Twenty-eight hypersensitivity studies were reviewed for difference in treatment effect (change from baseline) of actives and several reported differences between actives in VAS change from baseline of greater than 20 mm. Even with these notable differences, the authors routinely declare all actives effective in treatment of hypersensitivity. This study will use a more conservative non-inferiority margin of 15 mm. A standard deviation for change from baseline at immediately after treatment (within 15 minutes post-treatment) and 24-hours of 20 mm will be used. There is uncertainty in the efficacy difference between treatments as well as the error term. An interim analysis will be conducted at approximately 50% of subject treatment to reassess sample size with no alpha spending required. Ninety-six (96; 48 per arm) total subjects will provide 80% power allowing for a 2 mm difference in efficacy difference between treatments and 2 co-primary endpoints tested. No subjects will be lost to follow-up for the primary time point of immediate hypersensitivity relief, but there may be loss to follow-up for co-primary endpoint of hypersensitivity relief at 24-hours after treatment.

## **8.3. ANALYSIS POPULATIONS**

All dosed subjects without a major protocol deviation will be included in the analysis dataset for the co-primary endpoints of change in hypersensitivity immediately after product application and change in hypersensitivity 24-hours after application. For the secondary and exploratory endpoints, all dosed subjects without a major protocol deviation occurring up to the evaluation time for each endpoint will be included in the analysis dataset for that endpoint. All treated subjects will be included in the safety analysis dataset. Major protocol deviation(s) for exclusion from the analysis dataset will be defined and documented in a blinded fashion prior to interim and final analyses (eg, inadequate washout).

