### **6.6.10. Prohibited Procedures and On-Study Restrictions**

No other treatments for the study tooth other than those described in Section 6.6.6 are permitted during the course of this study. Any divergence from these treatment conditions will be captured as a protocol deviation (see Section 10) and the reason for selecting alternative treatments in the absence of an AE or device defect should be documented. Study visits that occur outside of the study visit windows will also be documented as protocol deviations. In addition, Subjects should avoid the following from the time of tooth treatment until completion of the study to ensure the oral hygiene activities and products used are controlled prior to and throughout the study:

- Refrain from additional desensitizing treatments after application of the study product.
- Refrain from activities that would impair the function of the products, including:
  - acidic beverages
  - use of any tooth whitening/bleaching products for the entire study period.

 HealthCare	CLINICAL INVESTIGATION PLAN	CLIN-PROT-CIP-11-050084 Version: 2 Status: Release
--	--	--

- Refrain from any non-emergency treatment for the entire study period.

Any deviation(s) from the CIP that diminishes the integrity of the data, results in non-adherence to the eligibility criteria, or impacts the Subject's rights, safety, or welfare will be documented as major protocol deviation(s) (see Section 10).

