## **8.7. PROCEDURES FOR MISSING, UNUSED, OR SPURIOUS DATA**

If a subject withdraws, only the data up to withdrawal will be used. There will be no imputation of missing outcome data. Any non-use of data will be explained and justified in the final report.

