**Table 10.1-1. Deviation reporting timelines and methods**

Type of Deviation	Report to Sponsor	Method
Major Subject safety, rights or welfare; OR Compromise the data integrity or statistical analysis of the study; OR Non-adherence to Inclusion/Exclusion criteria	Within 24 hours of study staff becoming aware of event	Initial: Phone/Email to Sponsor Complete CRF
All other protocol deviations	Per CIP-designated visits	Complete CRF

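### Section 8.3 puts no time limit on the deviations that remove a subject from the co-primary analyses, and no supportive all-treated efficacy analysis is planned

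*Combined protocol and SAP*

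**What the plan says.** Section 8.3 defines the efficacy datasets in two consecutive sentences.

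- Co-primary endpoints (15 minutes and 24 hours): "All dosed subjects without a major protocol deviation will be included in the analysis dataset for the co-primary endpoints". One dataset serves both time points, and the timing of the deviation is not mentioned.
- Secondary and exploratory endpoints: "all dosed subjects without a major protocol deviation occurring up to the evaluation time for each endpoint". Here the exclusion is limited in time, endpoint by endpoint.

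On which deviations count, section 8.3 adds: "Major protocol deviation(s) for exclusion from the analysis dataset will be defined and documented in a blinded fashion prior to interim and final analyses". Its one example, inadequate washout, precedes treatment.

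The on-study restrictions in section 6.6.10 run from treatment to study completion. One of them reads "Refrain from additional desensitizing treatments after application of the study product". On treatment of the study tooth outside the plan, the section says: "Any divergence from these treatment conditions will be captured as a protocol deviation". Section 6.6.10 and Table 10.1-1 define a major deviation without reference to time. One criterion in the table is "Compromise the data integrity or statistical analysis of the study".

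For withdrawals, section 8.7 says: "If a subject withdraws, only the data up to withdrawal will be used". It plans no imputation and requires any non-use of data to be justified in the report.

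The only all-treated set is for safety: "All treated subjects will be included in the safety analysis dataset". Sections 8.4.2 to 8.4.4 and 8.7 name no all-treated or sensitivity analysis of efficacy.

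**The concern.** The time limit is present for the less important endpoints and absent for the ones that decide the trial. Taken at its word, the co-primary rule lets an event in the following weeks delete a score recorded within 15 minutes or at 24 hours.

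Such a deletion is unlikely to be neutral. A subject who got little relief has more reason to seek other desensitising treatment before day 30. If that deviation is classed as major and listed as excluding, poor responders leave the co-primary analysis, and more of them leave from the worse arm. The observed difference shrinks and non-inferiority becomes easier to claim. Agreeing the exclusions blind to arm does not prevent this, because the outcome itself drives the deviation.

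The risk concerns subjects who remain in the study and deviate, since those who withdraw keep their earlier data. With no all-treated efficacy analysis, the report would not show whether exclusions of any kind had changed the conclusion.

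**Working it through.** **1. The rules applied to the same subject**

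| Event | 15-min and 24-h analyses | Day 7 analysis |
|---|---|---|
| Only major deviation on day 15, stays in study | Excluded (literal reading of 8.3) | Included |
| Withdraws on day 15, no major deviation | Included (8.7) | Included |
| Only major deviation between 15 min and 24 h | Excluded from both, including the earlier 15-minute score | Excluded |

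The first two rows treat equally valid early scores differently, and the plan gives no reason for it.

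**2. The plan's own figure**

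Inputs from section 8.2: margin 15 mm, SD 20 mm, true difference 2 mm, 48 per arm, 80% power. Section 8.4.2 gives a 97.5% interval at the stricter Hochberg step (one-sided 0.0125).

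- Standard error = 20 × √(2/48) = 4.08 mm
- Noncentrality = (15 − 2)/4.08 = 3.18
- Critical t (94 df, one-sided 0.0125) = 2.28
- Power by noncentral t = 81.6%

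The stated 80% is reproduced. The point below does not dispute it.

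**3. Size of the possible bias**

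The documents give no rate of late exclusion, so the following are assumptions: control mean reduction 30 mm; a subject with a reduction below 5 mm is excluded with probability p, the same in both arms. SD (20 mm) and n (48 per arm) come from section 8.2. Change is taken as reduction, and the difference is control minus test. The true difference is set at the 15 mm margin, so the test mean is 15 mm.

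For an arm with mean μ, let z = (5 − μ)/20.

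- Share excluded = p·Φ(z)
- Mean of those kept = [μ − p(μΦ(z) − 20φ(z))]/[1 − pΦ(z)]

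Control: z = −1.25, Φ = 0.1056. Test: z = −0.50, Φ = 0.3085. At p = 0.25:

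- Excluded: 0.25 × 0.1056 = 2.6% of control; 0.25 × 0.3085 = 7.7% of test
- Means of those kept: 30.94 and 16.91 mm
- Observed difference = 30.94 − 16.91 = 14.03 mm instead of 15

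Type I error was simulated (200,000 replicates per scenario; pooled-variance t; success if the upper limit of the two-sided 95% interval is below 15 mm):

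| p | Excluded, control / test | Mean difference | One-sided type I error, one endpoint |
|---|---|---|---|
| 0 | 0 / 0 | 15.0 mm | 2.5% |
| 0.05 | 0.5% / 1.5% | 14.8 mm | 2.7% |
| 0.10 | 1.1% / 3.1% | 14.6 mm | 3.1% |
| 0.15 | 1.6% / 4.6% | 14.5 mm | 3.4% |
| 0.25 | 2.6% / 7.7% | 14.0 mm | 4.3% |
| 0.50 | 5.3% / 15.4% | 12.8 mm | 8.1% |

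**4. Both co-primaries under Hochberg**

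True difference 15 mm on both; within-subject correlation 0.3, 0.5 or 0.7 (assumed); exclusion triggered by a 24-hour reduction below 5 mm and removing both scores; 100,000 replicates. Chance of any false claim:

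- p = 0: 2.3–2.4%
- p = 0.05: 2.5–2.6%
- p = 0.10: 2.7–2.9%
- p = 0.25: 3.7–3.8%
- p = 0.50: 6.6–6.7%

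**5. At the planned 2 mm difference**

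With a test mean of 28 mm, the same formula gives an expected difference of 1.95 mm at p = 0.10 and 1.87 mm at p = 0.25. The shifts are about 0.05 and 0.13 mm.

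**The case against.** The strongest reply is that the literal reading may never operate. Exclusions follow a list still to be drawn up blind. That list can carry the time limit, and its only example precedes treatment. For harm to occur, a subject must stay in the study and deviate after 24 hours, the deviation must be classed as major, and it must be listed as excluding for scores already taken. Subjects have agreed to withhold desensitising treatment, and a reviewer has little reason to think that treatment on day 10 spoils a 15-minute score. Section 8.7 also requires any unused data to be justified.

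Much of this stands. Off-protocol treatment is not automatically major, the wording may be a drafting slip, and p is the joint probability of several steps, so high values are hard to credit. At p = 0.10 about two subjects are lost in total (48 × 1.1% + 48 × 3.1% ≈ 2.0). The single-endpoint figures also tie exclusion to that endpoint's own score, which is the strongest possible link.

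It does not close the gap. Nothing in section 8.3 limits the list by time for the co-primaries, and blinding does not remove exclusion driven by outcome. A written justification does not show the result with the data included. The simulation does not quantify the missing supportive analysis once exclusions are time-limited. That part rests on the plan naming only one kind of efficacy set, and it holds even if no late deviation is ever listed.

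**Conclusion.** The concern holds and should be fixed. That the time limit is missing for the co-primaries, and that no all-treated efficacy analysis is planned, is certain from the text. The bias is conditional. It is small if few poor responders are excluded (any false claim 2.7–2.9% at p = 0.10, against 2.3–2.4% with none) and material only if many are and the true difference is near 15 mm. At the planned 2 mm difference it is negligible. These sizes rest on the assumed 30 mm control mean, 5 mm cut-off, correlations and values of p. No figure in the plan is shown to be wrong.

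**What to change.** 1. In section 8.3, define the co-primary datasets separately, in the same way as the secondary ones. For example: for each co-primary endpoint, include every dosed subject with no major deviation by the time that endpoint is measured (within 15 minutes, or 24 ± 4 hours).
2. Add a supportive analysis for each co-primary endpoint in all randomised and treated subjects with the relevant VAS score, analysed as randomised with the same confidence interval. Report it beside the primary result. It need not be a pass criterion.

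The cost is one phrase and one more run of the same analysis. The time limit can only add subjects to the co-primary datasets. The one drawback is that, if the two sets disagree, the report must explain why.

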## **8.4. STATISTICAL ANALYSES**

### **8.4.1. Demographic and Baseline Characteristics**

Demographic and baseline characteristics for the study will be generated and displayed by treatment arm and overall. Key baseline characteristics variables may include but are not limited to general health status, baseline pain, and any specific factors that may affect the change in pain after treatment.

### **8.4.2. Analysis of Primary Endpoints**

At the final analysis, multiplicity will be controlled through a Hochberg procedure. Ninety-five- percent (95%) confidence intervals will be generated for the difference between treatments

in change from baseline immediately after application and separately for the difference between treatments in change from baseline 24-hours after application using Student's t distribution.

Scenario 1: Neither of the 95% confidence intervals contain 15 mm.

Result: Non-inferiority for both co-primary endpoints will be declared

Scenario 2: Both of the 95% confidence intervals contain 15 mm.

Result: No non-inferiority for either co-primary endpoints will be declared, and all analyses will be informational only.

Scenario 3: One confidence interval contains 15 mm, and the other confidence interval does not contain 15 mm.

The endpoint that does not contain 15 mm has the potential to be declared non-inferior. For this endpoint, as part of the Hochberg procedure, a 97.5% confidence interval will be generated. Non-inferiority for this endpoint will be declared if the new confidence interval does not contain 15 mm.

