In 2003, Corona et al reported the number of Subjects (n = 30) within each Schiff category in response to air blast stimulus both before and immediately after application of a 5% F varnish. Before treatment, there were no (0) Subjects with a score of “0”, 11 Subjects with a score of “1”, 13 Subjects with a score of “2”, and 6 with a score of “3”. Immediately after treatment, 11 Subjects had a score of “0”, 6 had a score of “1”, ten had a score of “2”, and 3 had a score of “3”. In 2018, Anderson et al analyzed the immediate impact of a 5% F varnish on immediate changes in DHS by analyzing both the VAS and Schiff score upon air blast stimulus for 11 Subjects. The mean ( $\pm$  SD) VAS was reduced from 58.18 mm ( $\pm$  15.16 mm) at pre-treatment to 30.5 mm ( $\pm$  28.51 mm) after treatment, and the mean ( $\pm$  SD) Schiff score was reduced from 2.32 ( $\pm$  0.72) at pre-treatment to 0.91 ( $\pm$  1.0) after treatment (P < 0.05). In a study of 36 teeth treated with a 5% F varnish, Eyüboğlu et al showed a significant reduction in VAS upon air blast stimulus (P < 0.001), changing from 56.39 mm ( $\pm$  19.91) at baseline to 10 mm ( $\pm$  15.11 mm) immediately after treatment. Additionally, there was significant change in the amount of pressure (ie, tactile stimulus) before the Subject felt discomfort (P < 0.01), changing from 18.89 g ( $\pm$  12.1 g) at baseline to 32.78 g ( $\pm$  23.49 g) immediately after treatment. Finally, Machado et al observed a significant reduction in VAS (P < 0.05) in response to air blast stimulus, with a mean ( $\pm$  SD) VAS of 5.9 cm ( $\pm$  1.5 cm) at baseline versus 3.4 cm ( $\pm$  2.4 cm) immediately after treatment. In this study, a significant reduction in VAS (p < 0.05) was also seen for teeth (n = 38) treated with a F-containing ionomeric sealant, with a mean ( $\pm$  SD) VAS of 6.7 cm ( $\pm$  1.7 cm) at baseline and 3.4 cm ( $\pm$  2.5 cm) immediately after treatment.

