**Table 6.5.1-1: Inclusion Criteria**

Number	Inclusion Criteria
1	Subject has at least one affected hypersensitive tooth upon air blast stimuli in the cervical area, and baseline pain score of 40 mm and above as assessed by the 100 mm VAS.
2	Subject is at least 18 years old and have a minimum of 20 natural teeth.
3	Subject is willing to withhold desensitizing treatment, including prescription, in-office or over the counter (OTC) desensitizing products, throughout the study period AND withhold during the washout period
4	Subject agrees to only use the provided toothpaste, toothbrush, and follows all oral hygiene instructions throughout the study period AND follows all oral hygiene instructions during the washout period.
5	Subject is able to understand and willing to sign the Informed Consent, and is willing to return to the study facility for scheduled study visits and recalls.

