#### **6.6.3. Demographics and Subject Characteristics**

After a Subject signs the ICF but before treatment, the following demographic data and Subject characteristics will be collected and documented:

- Age
- Sex
- Baseline VAS upon air blast and tactile stimuli immediately before treatment
- Race
- Ethnicity
- Study tooth number

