**Table 6.7.2.1-1: Schedule**

	Consenting Visit & pre-treatment washout	Treatment Visit	24-hour follow- up	Day 7 follow- up	Day 21 follow-up	30 Day follow-up	Unscheduled Visit
Visit Number	1	2	3	4	5	6	
Visit Window	3-6 weeks	Day 0	24 ± 4 h	7 d ± 2 d	21 d ± 2 d	30 d ± 2 d	
Screening	X						
Informed Consent signed	X						
Concomitant meds	X	X	X	X	X	X	X
Eligibility confirmation	X	X*					
Enrollment	X						
Randomization		X					
DHS Treatment		X					
Pain assessments to air-blast stimulus and tactile stimulus	X	X**	X	X	X	X	X
AEs / SAEs / ADEs / DDs		X	X	X	X	X	X
End-of-Study						X	X***

\* Before treatment

\*\*Before treatment (baseline) and after treatment

\*\*\*if applicable

 HealthCare	CLINICAL INVESTIGATION PLAN	CLIN-PROT-CIP-11-050084 Version: 2 Status: Release
--	--	--

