#### **8.4.3. Analysis of Secondary Endpoints**

If the null hypotheses are rejected for both co-primary endpoints, the alpha will be passed to test for non-inferiority of Clinpro™ 2.1% Sodium Fluoride Aqueous Solution to Vanish™ Varnish for the various secondary endpoints. Ninety five percent (95%) confidence intervals will be generated for the difference between treatments in change from baseline using the Student's t distribution at each evaluation time. Non-inferiority will be declared if Vanish™ Varnish changed from baseline minus Clinpro™ 2.1% Sodium Fluoride Aqueous Solution change from baseline is less than or equal to 15 mm for each secondary endpoint. There are 3 secondary endpoints. The alpha will be passed sequentially in the order listed in section 5.3.2.

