## **8.5. PLANNED INTERIM ANALYSES AND CRITERIA FOR CLINICAL INVESTIGATION**

An interim analysis will be conducted after treating approximately 50% of the planned sample size for the purpose of sample size re-estimation. No alpha will need to be spent because of this sample size re-estimation. The parameter estimates from the interim data will be used and the sample size necessary for 80% power will be calculated.

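### The efficacy comparisons leave out the Visit 2 baseline VAS; a prespecified baseline-adjusted ANCOVA would cost almost nothing, for a gain of uncertain size

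*Combined protocol and SAP*

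**What the plan says.** Section 8.4.2 bases both co-primary decisions on 95% confidence intervals from the t distribution: one for the difference between arms in change immediately after application and, "separately for the difference between treatments in change from baseline 24-hours after application", a second. A 97.5% interval is added when only one endpoint passes. Section 8.4.3 does the same for the secondary endpoints, where "confidence intervals will be generated for the difference between treatments in change from baseline", and Section 8.4.4 repeats it for the exploratory tactile endpoints. None of these sections names a covariate or a model.

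The baseline score exists for every treated subject. Section 6.6.3 lists "Baseline VAS upon air blast and tactile stimuli immediately before treatment", and the footnote to Table 6.7.2.1-1 places the Visit 2 pain assessments "Before treatment (baseline) and after treatment". The plan's only use for it outside the change score is in Section 8.4.1, which tabulates by arm "baseline pain, and any specific factors that may affect the change in pain after treatment".

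Section 8.2 sets a 15 mm margin, a 20 mm SD of change, a 2 mm true difference and 48 subjects per arm for 80% power. Section 8.5 re-estimates the sample size at about half of the planned treatments: "The parameter estimates from the interim data will be used and the sample size necessary for 80% power will be calculated".

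**The concern.** A raw change score amounts to assuming that each extra millimetre of baseline VAS carries through as one extra millimetre afterwards, that is, a slope of 1. At any other slope, some of the spread in change is explained by baseline and could be removed. The unadjusted interval is then wider than it need be. In the single trial that is run, a fraction (1 − slope) of any chance baseline difference between arms also passes into the estimate.

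Non-inferiority turns on one confidence limit, with 15 − 2 = 13 mm between the assumed difference and the margin, and planned power is close to its 80% target. Section 8.2 itself says that the error term is uncertain. What is at stake is efficiency. There is no added risk of a false non-inferiority claim.

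**Working it through.** **1. The plan's own figure.** The inputs are those of Section 8.2. The standard error of the difference is 20 × √(2/48) = 4.08 mm, and the gap in standard errors is 13/4.08 = 3.18. By the noncentral t with 94 df:

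- One-sided 0.025 (the 95% interval): 88.3% power per endpoint.
- One-sided 0.0125 (the 97.5% interval): 81.6% per endpoint. Eighty percent needs 47 per arm, or 94 in total, against 96 planned.
- Both endpoints passing at 0.025, by simulation: 78.0%, 79.4%, 80.6% and 82.2% for a correlation between endpoints of 0, 0.3, 0.5 and 0.7.

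The stated 80% therefore reproduces without adjustment.

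**2. What adjustment does.** Write b and p for the SDs before and after treatment, r for their correlation and d for the SD of change.

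- d² = b² + p² − 2rbp, so r = (b² + p² − d²)/(2bp)
- slope = r·p/b
- ANCOVA residual SD = √(d² − (1 − slope)²·b²)

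**3. Inputs for r (assumption).** The documents give no r. I set d = 20 mm and took b and p from the three studies in Section 2.1.2.2 that report VAS SDs before and immediately after a varnish. The entry rule requires a "baseline pain score of 40 mm and above as assessed by the 100 mm VAS", so I also cut a normal baseline with each study's mean and SD to 40–100 mm. That lies 10%, 12% and 21% below 40 before the cut. Slope and d = 20 were held.

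| | Placebo-controlled study | 11-subject study | 36-tooth study |
|---|---|---|---|
| Baseline mean, mm | 59 | 58.18 | 56.39 |
| SD before / after, mm | 15 / 24 | 15.16 / 28.51 | 19.91 / 15.11 |
| r | 0.557 | 0.743 | 0.373 |
| Slope | 0.89 | 1.40 | 0.28 |
| Residual SD, no cut | 19.93 | 19.07 | 14.02 |
| Variance reduction, no cut | 1% | 9% | 51% |
| Baseline SD after the cut | 12.38 | 12.35 | 14.04 |
| Residual SD after the cut | 19.95 | 19.39 | 17.28 |
| Variance reduction after the cut | 0.5% | 6% | 25% |
| Power, one-sided 0.0125 (unadjusted 81.6%) | 81.8% | 84.1% | 91.8% |
| Power, one-sided 0.025 (unadjusted 88.3%) | 88.5% | 90.2% | 95.4% |
| 97.5% half-width, mm (unadjusted 9.30) | 9.28 | 9.02 | 8.04 |
| n per arm for 80% at 0.0125 (unadjusted 47) | 47 | 44 | 35 |

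Example, third column after the cut: √(400 − (1 − 0.283)² × 14.04²) = 17.28. Two slopes lie below 1 and one above, so the inputs do not agree even on direction.

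**4. The same gain seen as a baseline shift.** A chance baseline difference of one standard error, SD × √(2/48), moves the raw estimate by |1 − slope| times that amount. After the cut this is 0.3, 1.0 or 2.1 mm.

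**5. The cost if baseline is useless.** Estimating one slope uses 1 df and inflates the variance by an expected 1 + 1/(96 − 4) = 1.011. The 95% half-width goes from 8.11 to 8.15 mm (about 0.5%), and power at 0.0125 from 81.6% to 81.1%. The adjusted powers in the table use 93 df but leave out this inflation. With it, the variance ratios after the cut are 0.9955 × 1.011 = 1.006, 0.940 × 1.011 = 0.950 and 0.747 × 1.011 = 0.755. The net result is therefore a trivial loss, a 5% gain or a gain of about 24%.

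**6. Sensitivity of step 3.** With slope and residual SD held through the cut instead of d, the largest reduction is 34%, but unadjusted power for that pair is then already 91.9%. With d = 25 mm instead of 20, the reductions without the cut change from 1%, 9% and 51% to 13%, 0.3% and 63%.

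**The case against.** The strongest reply is that nothing is broken. The planned interval is valid, the sample size reproduces, and the choice is between two sound estimators. That is correct, and it limits this point to a recommendation.

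Several narrower objections also stand:

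- The narrower interval and the protection against a chance baseline difference are one benefit. In the third column (2.05/4.08)² = 25%, which is the variance reduction itself. They should not be counted twice.
- At the first Hochberg step (95% intervals) the gains are smaller: about 0.1, 1.8 and 7.1 points.
- The correlations are constructed from other studies' SDs and this plan's d, and they move when d moves. One study has 11 subjects and another counts teeth. The cut at 40 mm assumes a normal baseline and no entry threshold in the cited samples.
- The only large gain comes from a study with a post-treatment mean of 10 mm and an SD of 15.11 mm on a scale bounded at zero, where a straight-line slope is least secure.
- That the plan is unadjusted is inferred. The text names the t distribution, which an ANCOVA interval also uses, although no covariate appears anywhere.
- Adjusting the exploratory endpoints adds little, since no claim is made on them.

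Interim re-estimation, with enrolment of up to 125, does cushion power. It does so by adding subjects, and it does not recover efficiency at a given N. None of these objections makes the change unsound.

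**Conclusion.** The point holds as a low-cost improvement, not as the correction of an error. Under the 40 mm entry rule, the literature-based inputs give anything from no gain to a variance reduction of about 25%. That is up to 10 points of power per endpoint at one-sided 0.0125 and up to 7 at 0.025. The worst case is about half a point of power.

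The size rests on an assumed correlation between baseline and post-treatment scores, a 20 mm SD of change, a linear relation and a normal baseline cut at 40 mm. The documents cannot settle it, and a gain near zero is possible. The recommendation rests on the bounded cost and on the covariate already being collected, not on any one figure in the range.

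**What to change.** Before the interim look:

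- **8.4.2 and 8.4.3:** prespecify an ANCOVA of change on arm with the Visit 2 pre-treatment air-blast VAS as covariate. Name the visit, because Table 6.7.2.1-1 also schedules a pain assessment at Visit 1. Compare the confidence limit of the adjusted difference with 15 mm, leaving the margin, the Hochberg steps and the order of secondary tests as they are.
- **8.4.4:** use the Visit 2 tactile VAS in the same way, for consistency only.
- **8.5:** base the re-estimation on the ANCOVA residual SD, so that the interim calculation matches the final analysis.
- **Sensitivity analysis:** keep the unadjusted t interval.

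The timing matters because the investigator is not blinded and the interim uses observed estimates; adjustment chosen after that look would be open to challenge. The cost is wording in four sections and 1 degree of freedom, with no extra subjects or data.
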